10.4 Secondary Efficacy Analyses

The following analyses of secondary efficacy endpoints will be performed on the ITT-II population:

- The percentage of subjects achieving SVR₁₂ (HCV RNA < LLOQ 12 weeks after the last actual dose of study drug). The simple percentage of subjects

achieving SVR₁₂ will be calculated and a two-sided 95% confidence interval of the percentage will be computed based on Wilson's score method.

- The mean change from baseline in quality of life and fatigue to Post-Treatment Week 12 and to the Post-Treatment Week 24 (assessed by Short-Form 36 Version 2 health survey [SF-36v2] and the Functional Assessment of Chronic Illness Therapy – Fatigue [FACIT–F] questionnaires, respectively) will be assessed by subjects' baseline fibrosis stage, as described in Section 10.8.
- Adherence to ABT-450/r/ABT-267 and ABT-333 combined and adherence to RBV within the Treatment Period will be calculated as the percentage of tablets taken relative to the total tablets expected to be taken, as described in Section 9.2.

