5.3.2.2 Secondary Variables

The secondary endpoints are:

- The percentage of subjects with SVR₁₂ (HCV RNA < LLOQ 12 weeks after the last actual dose of study drug);
- The mean change from baseline in quality of life and fatigue to Post-Treatment Week 12 and Post-Treatment Week 24 (assessed by Short Form 36 Version 2 health survey (SF-36v2) and the Functional Assessment of Chronic Illness Therapy – Fatigue (FACIT-F) questionnaires).
- Adherence to the prescribed regimen (measured by pill counts for each type of tablet).

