5.5.7 Drug Accountability

The investigator or his/her representative will verify that study drug supplies are received intact and in the correct amounts using the IRT system. A current (running) and accurate inventory of study drug will be kept by the investigator or his/her designated and qualified representatives and will include lot number, number of tablets dispensed, subject number, username of person who dispensed study drug and date dispensed for each subject. Final accountability will be verified by the monitor at the end of study drug treatment at the site.

During the study, should an enrolled subject misplace or damage a study drug kit, the IRT system must be contacted and informed of the misplaced or damaged study drug. If the kit is damaged, the subject will be requested to return the remaining study drug to the site. Replacement study drug may only be dispensed to the subject by contacting the IRT system. Study drug replacement(s) and an explanation of the reason for the misplaced or damaged study drug(s) will be documented within the subject source documentation.

Study drug start dates for each drug and the last dose of the regimen will be documented in the subject's source documents and recorded on the appropriate eCRF. The status of each kit, number of tablets remaining in each one returned, and the date of reconciliation will be documented in the IRT system at Study Visits defined as Study Drug Returned for IRT Reconciliation in [Table 7](#). The monitor will review study drug accountability on an ongoing basis.

Upon completion of or discontinuation from the Treatment Period, all original study drug bottles (containing unused study drugs) will be returned to the Sponsor (or designee) or destroyed on site. All destruction procedures will be according to instructions from the Sponsor and according to local regulations following completion of drug accountability

procedures. The number of tablets of each type of study drug returned in each kit will be noted in the IRT system. Labels must remain attached to the containers.

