8.1.2.2 Secondary Efficacy Endpoints

The secondary efficacy endpoints are:

1. The percentage of subjects achieving SVR₁₂ (HCV RNA < LLOQ 12 weeks after the last actual dose of study drug). The simple percentage of subjects achieving SVR₁₂ will be calculated and a two-sided 95% confidence interval of the percentage will be computed using the Wilson score method for the binomial proportion.
2. The mean change from baseline in quality of life and fatigue to Post-Treatment Week 12 and to the Post-Treatment Week 24 (assessed by Short-Form 36 Version 2 health survey [SF-36v2] and the Functional Assessment of Chronic Illness Therapy – Fatigue [FACIT–F] questionnaires) will be assessed by subjects' fibrosis stage at baseline.

Summary statistics (n, mean, SD, minimum and maximum) at Baseline and each applicable visit will be provided. In particular, the comparison of the mean change from baseline to Post-Treatment Week 12 and to Post-Treatment Week 24 in the SF-36v2 Vitality domain score, SF-36v2 Mental Component Summary Score and Physical Component Summary score and in the FACIT-F score among subjects who had different fibrosis stage at baseline will be performed using ANCOVA analyses with baseline fibrosis stage (F0-F1, F2, F3 and F4) as factor and baseline PRO score and SVR₁₂ status as covariates.

3. Adherence to each tablet type (ABT-450/r/ABT-267, ABT-333, and RBV) during the Treatment Period will be calculated as the percentage of tablets taken relative to the total tablets expected to be taken for each tablet type.

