4.0 Study Objectives, Design and Procedures

4.1 Objectives

The primary objective of this study is to evaluate the effect of virologic response to treatment (assessed by SVR₁₂ status) on the long-term progression of liver disease in adults with chronic HCV GT1 infection who receive treatment with ABT-450/r/ABT-267 and ABT-333 with or without ribavirin, as measured by all-cause death, liver-related death, liver decompensation, liver transplantation, and hepatocellular carcinoma.

The secondary objectives are to evaluate the sustained virologic response in adults with GT1 chronic HCV infection who receive ABT-450/r/ABT-267 and ABT-333 with or without ribavirin, to assess the change from baseline in quality of life and fatigue following treatment assessed by Short-Form 36 Version 2 health survey (SF-36v2) and the Functional Assessment of Chronic Illness Therapy – Fatigue (FACIT-F) questionnaires, respectively) by baseline fibrosis stage, and to assess adherence to the prescribed regimen (measured by pill counts for each type of tablet). Sustained virologic response is evaluated by the percentage of subjects achieving SVR₁₂.

[figure not shown]

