9.2 Compliance

At each protocol-specified visit, the total number of tablets dispensed and returned is recorded together for ABT-450/r/ABT-267 and ABT-333, and is recorded separately for RBV. The compliance for ABT-450/r/ABT-267 and ABT-333 combined and the compliance for RBV within the Treatment Period will be calculated as the percentage of tablets taken (presumed as [tablets dispensed-tablets returned]) relative to the total capsules or tablets, respectively, expected to be taken. The total number of tablets prescribed will be equal to the total number of tablets that should have been taken per the protocol for the duration that the subject was in the Treatment Period (date of last dose – date of first dose + 1 day). Study drug interruptions due to an adverse event or other planned interruptions recorded on the eCRF will be subtracted from the duration. For compliance to RBV, RBV dose modifications due to adverse events, toxicity management, or weight changes as recorded on the RBV Dose Modifications eCRF will be used to modify the total number of tablets that should have been taken. A subject is considered to be compliant if the percentage is between 80% and 120%. Compliance will

be calculated for each subject and summarized with the n, mean, median, SD, minimum, and maximum. In addition, the percentage of compliant subjects will be calculated separately for ABT-450/r/ABT-267 + ABT-333, and RBV.

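### The SAP pools the two DAA tablets in an adherence endpoint the protocol defines by tablet type, and leaves out the protocol's PRO ANCOVA by fibrosis stage

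*SAP*

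**What the plan says.** **Adherence.** Protocol 5.3.2.2 lists as a secondary endpoint "Adherence to the prescribed regimen (measured by pill counts for each type of tablet"). Protocol 8.1.2.2 gives the calculation and names the types: "Adherence to each tablet type (ABT-450/r/ABT-267, ABT-333, and RBV) during the Treatment Period will be calculated" as tablets taken over tablets expected, for each type. The SAP's own objective (4.1) is "to assess adherence to the prescribed regimen (measured by pill counts for each type of tablet").

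SAP 10.4 then specifies "Adherence to ABT-450/r/ABT-267 and ABT-333 combined and adherence to RBV within the Treatment Period", calculated as in SAP 9.2. That section says dispensed and returned counts are "recorded together for ABT-450/r/ABT-267 and ABT-333", with RBV recorded separately. It calls a subject compliant between 80% and 120%, and "the percentage of compliant subjects will be calculated separately for ABT-450/r/ABT-267 + ABT-333, and RBV".

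On data capture, Protocol 5.5.7 says: "The number of tablets of each type of study drug returned in each kit will be noted in the IRT system".

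**Patient-reported outcomes (PRO).** The protocol synopsis and 8.1.2.2 specify an ANCOVA of change from baseline to Post-Treatment Weeks 12 and 24. Baseline fibrosis stage is the factor; baseline PRO score and SVR12 status are covariates. Protocol 8.1.2.2 names four scores: SF-36v2 Vitality, Mental Component Summary (MCS), Physical Component Summary (PCS), and FACIT-F. SAP 10.4 keeps the endpoint by fibrosis stage but refers to Section 10.8 for the method. Section 10.8 is Resistance Analyses. The PRO section is 10.9; it lists analyses labelled exploratory, with no ANCOVA and no breakdown by fibrosis stage.

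**The concern.** The pooled percentage is a different quantity from the endpoint in Protocol 8.1.2.2, and the SAP is also at odds with its own objective in 4.1. ABT-333 is the only DAA with an evening dose (Protocol 5.5.2.1 and 5.5.4), so missed evening doses lower ABT-333 adherence and leave ABT-450/r/ABT-267 untouched. Pooling halves that shortfall and makes it look the same as missing whole days. The study itself treats morning and evening doses as distinct: care plan levels differ in once- or twice-daily reminders, and the web portal may be used to check both doses (Protocol 5.3.1.1).

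For the PRO endpoint, SAP 4.4 says analyses will follow the methods in the SAP. A programmer working from it would find no model for the comparison by fibrosis stage, and would find PRO analyses described only as exploratory.

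At stake is the reporting of two secondary endpoints.

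**Working it through.** **Inputs**
- ABT-450/r/ABT-267: 2 tablets once daily. ABT-333: 1 tablet twice daily (Protocol 5.5.1).
- Weekly card: 7 days plus 1 spare day, 16 + 16 = 32 tablets (Protocol 5.5.2.1).
- Compliance band: 80% to 120% (SAP 9.2).
- Assumption: 84 days (or 168) from first to last dose, with no recorded planned interruption.

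**Check of the plan's own figure.** 8 days × (2 + 2) tablets = 32 per card, as stated. The two products carry equal weight.

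**Formula.** With a₁ = ABT-450/r/ABT-267 adherence and a₂ = ABT-333 adherence, pooled = (2a₁ + 2a₂)/4 = (a₁ + a₂)/2.

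**Tablets due over 84 days.** 2 × 84 = 168 of each, 336 pooled.

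**Two patterns with the same pooled value**

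| Pattern | ABT-450/r/ABT-267 | ABT-333 | Pooled |
|---|---|---|---|
| 32 evening doses missed | 168/168 = 100% | 136/168 = 81.0% | 304/336 = 90.5% |
| 8 whole days missed | 152/168 = 90.5% | 152/168 = 90.5% | 304/336 = 90.5% |

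**Effect on the SAP's compliance band, with ABT-450/r/ABT-267 taken in full**
- Pooled 80% limit: 0.8 × 336 = 268.8, so 269 tablets (80.06%).
- Lowest ABT-333 count still classed compliant: 269 − 168 = 101 of 168 (60.1%).
- 80% limit on ABT-333 alone: 0.8 × 168 = 134.4, so 135 tablets.
- The two classifications therefore differ for 101 to 134 tablets (60.1% to 79.8%).
- If all missed tablets are evening doses, that is 34 to 67 of 84 missed (40.5% to 79.8%).
- If every evening dose is missed, a₂ = 50% and pooled = 75%, which falls below the band.

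**24 weeks.** 336 of each, 672 pooled. The limit is 538 (0.8 × 672 = 537.6), so the lowest count is 538 − 336 = 202. The limit on ABT-333 alone is 269, so the classifications differ for 202 to 268 of 336.

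**PRO.** 4 scores × 2 visits = 8 ANCOVA comparisons named in Protocol 8.1.2.2. None appears in SAP 10.4, 10.8 or 10.9.

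**The case against.** The best defence of pooling is data capture. SAP 9.2 says the DAA counts are recorded together, and both tablets share one card. Protocol 5.5.6 groups the two DAA tablets in a similar way. The sentence in Protocol 5.5.7 on counts by type stands in the paragraph on returns at the end of treatment, while the same section describes visit-level recording by kit without mentioning type. Protocol 5.3.1.1 can be read either way. This stands as far as it goes: the documents do not settle whether counts by type exist. It does not rescue the SAP, because a count by type for each kit, whenever made, would be enough for an endpoint covering the whole Treatment Period. If no such counts exist, the SAP should say that the protocol endpoint cannot be computed.

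Separate percentages are spelled out only in Protocol 8.1.2.2; Protocol 5.3.2.2 and SAP 4.1 describe pill counts by tablet type. That is correct, but 8.1.2.2 is the operative definition and SAP 10.4 departs from it.

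The numbers are illustrations. No adherence data are given, the misclassification range needs a marked pattern, and card markings, counselling and reminders all work against it. If tablets are mostly missed as whole days, the pooled and by-type figures agree. The compliance band is also the SAP's own addition, not part of the protocol endpoint. These points limit the likely size of the effect and are accepted.

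The PRO reference may be only a numbering slip, and the protocol still fixes the model. Correcting the number would still lead to a section without the analysis. Some would rank this point at least level with adherence, since a secondary endpoint has lost its model in the SAP.

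Finally, Protocol 5.6.1 calls the analyses descriptive, while Protocol 8.1 and SAP 10.1 set a two-sided 0.05 level. The finding does not depend on which reading prevails.

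**Conclusion.** The concern holds. SAP 9.2 and 10.4 produce two adherence percentages where Protocol 8.1.2.2 requires three, and neither DAA tablet gets its own. RBV is handled separately in both documents and is not affected.

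The pooled figure is the mean of the two DAA percentages, so it halves any shortfall confined to ABT-333 and can class a subject as compliant at 60.1% ABT-333 adherence. The arithmetic rests on the daily tablet counts in Protocol 5.5.1 and on an uninterrupted 84- or 168-day course. The frequency of such patterns is unknown, and the effect may be small.

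The PRO point also holds: eight comparisons specified in the protocol have no analysis in the supplied SAP.

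Both matters should be corrected. They concern the reporting of secondary endpoints; the primary analysis, SVR12 and the sample size do not depend on them.

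**What to change.** **Adherence.** Establish what the IRT system holds, and reconcile SAP 9.2 with Protocol 5.5.7.
- If counts by tablet type exist, report the percentage separately for ABT-450/r/ABT-267, ABT-333 and RBV, and apply the SAP's 80% to 120% band in the same way. Keep the pooled DAA figure as supportive.
- If they do not, state that the protocol endpoint cannot be computed for the two DAA tablets, and report the pooled figure with that limitation.

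**PRO.** Change the reference in SAP 10.4 from 10.8 to 10.9. In 10.9 enter the protocol ANCOVA as a secondary analysis: Vitality, MCS, PCS and FACIT-F at Post-Treatment Weeks 12 and 24, fibrosis stage (F0-F1, F2, F3, F4) as factor, baseline PRO score and SVR12 status as covariates. Leave the other 10.9 summaries as exploratory.

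**Cost.** One check of the IRT data, then a few tables or one sentence of limitation; one corrected cross-reference, one paragraph, and eight ANCOVA outputs that the protocol already requires. No new data collection is needed.

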10.5 Efficacy Subgroup Analysis

The analysis on SVR₁₂ status as described in Section 10.4 will be performed on the ITT-II population for the following subgroups (assessed at baseline), as appropriate:

- The presence of cirrhosis and subgenotype (GT1b without cirrhosis, GT1b with compensated cirrhosis, GT1 non-b without cirrhosis, and GT1 non-b with compensated cirrhosis);
- prior treatment history (treatment-naïve [IFN-eligible, IFN-ineligible] or IFN/RBV treatment-experienced [null responder, partial responder, relapser, relapse/breakthrough, nonresponder, IFN or pegIFN intolerant]);
- IL28B ([CC, CT, TT] and [CC or non-CC]);
- Sex (male or female);
- Age (< 55 or ≥ 55 years) and (< 65 or ≥ 65 years);
- Birth year (< 1945, 1945 to 1965, > 1965);
- Race (Black or Non-Black; Black will include any subject who marks 'Black or African American' for race on the Demographics eCRF);
- Ethnicity (Hispanic or Latino, Not Hispanic or Latino);
- BMI (< 30 or ≥ 30 kg/m²);

- Baseline HCV RNA levels ($< 800,000$ or $\geq 800,000$ IU/mL; below median or above or equal to median);
- Baseline GFR by Cockcroft Gault (< 50 or ≥ 50 mL/min);
- Baseline GFR by MDRD (< 30 , $30 - 59$, $60 - 89$, ≥ 90 mL/min/1.73 m²; < 60 or ≥ 60 mL/min/1.73 m²);
- Baseline HOMA-IR (< 3 or ≥ 3 mU \times mmol/L²);
- History of Depression or Bipolar Disorder (yes/no);
- History of Bleeding Disorders (yes/no);
- Baseline Child-Pugh score (< 5 , 5 , 6 , or > 6);
- Baseline fibrosis stage (F0-F1, F2, F3, or F4);
- APRI (≤ 2.0 or > 2.0);
- FIB-4 (≤ 3.25 or > 3.25);
- Any of APRI > 2.0 and FIB-4 > 3.25 , or neither.

For subjects with cirrhosis only:

- Baseline platelets ($< 50 \times 10^9/L$ or $\geq 50 \times 10^9/L$; $< 90 \times 10^9/L$ or $\geq 90 \times 10^9/L$; $< 100 \times 10^9/L$ or $\geq 100 \times 10^9/L$; $< 150 \times 10^9/L$ or $\geq 150 \times 10^9/L$);
- Baseline albumin (< 35 or ≥ 35 g/L);
- Platelets $< 90 \times 10^9/L$ or albumin ≥ 35 g/L, or neither of the two.

For GT1 non-b subjects with cirrhosis only:

- Treatment Duration (12 weeks or 24 weeks).

Each subgroup analysis will be performed if there are an adequate number of subjects within each subgroup. The two-sided 95% Wilson score confidence interval for a binomial proportion (percentage of subjects achieving SVR₁₂) will be produced if there are at least 10 subjects in the subgroup.

In addition, stepwise logistic regression will be performed on both SVR₁₂ and virologic failure (on-treatment virologic failure or relapse) using subgroup variables described

above as predictors of response. Some variables will be treated as continuous to decrease the chance of separation or quasi-separation and some variables may be eliminated if missing for many subjects.

10.6 Sensitivity Analysis for the Efficacy Endpoint of SVR₁₂

In addition to presenting the secondary efficacy endpoint of SVR₁₂ as described in Section 10.4, two sensitivity analyses of SVR₁₂ will be presented using the following modified populations. The first sensitivity analysis of SVR₁₂ will be conducted using a Modified Intent-to-Treat Genotype (mITT-GT) population that includes subjects who receive at least 1 dose of study drug (with imputation as described in Section 6.3) but excludes the subjects who are not of HCV genotype 1 infection. The mITT-GT population is used to reduce the risk of bias that could occur due to enrolled population deviating from the protocol selected study population.

The other sensitivity analysis of SVR₁₂ will be conducted using a Modified Intent-to-Treat Genotype and Virologic Failure (mITT-GT + VF) population. The mITT-GT + VF population is used to reduce the risk of bias that could occur due to either discordant HCV genotype or irrelevant failures unrelated to study drug. The mITT-GT + VF population includes all subjects who receive at least 1 dose of study drug (with imputation as described in Section 6.3) but excludes the subjects who are not of HCV genotype 1 infection and the subjects who were categorized as "prematurely discontinued study drug with no on-treatment virologic failure" and "missing follow-up data in the PT Period."

10.7 Additional Efficacy Analyses

The following additional HCV RNA efficacy endpoints will be summarized and analyzed on the ITT-II population, as specified:

- The number and percentage of subjects with on-treatment virologic failure;
- The number and percentage of subjects with post-treatment relapse;
- The number and percentage of subjects with RVR;
- The number and percentage of subject with EOTR;

- The number and percentage with unquantifiable HCV RNA at each post-baseline visit throughout the Treatment Period (using data from the central laboratory as observed, i.e., no imputation for missing data);
- The percentage of subjects with HCV RNA < LLOQ 24 weeks after the last actual dose of study drug (SVR₂₄);
- Reasons for not achieving SVR₂₄ for subjects who do not;
- Mean change from baseline in prothrombin time/International normalized ratio (PT/INR), FibroTest and albumin to each applicable post-baseline time point;
- The number of subjects who fail to suppress and accompanying listing;
- The number of subjects who breakthrough any time during treatment and accompanying listing;
- The number of completers with final on-treatment HCV RNA < LLOQ who relapse within the SVR₄ window, SVR₁₂ window, or SVR₂₄ window and accompanying listing;
- The concordance between SVR₁₂ and SVR₂₄ will be assessed.

In the above analyses that use the number and percentage of responders, two-sided 95% Wilson score confidence interval for a binomial proportion will be calculated.

Imputations for missing data will be performed as described in Section 6.3 for analyses of SVR, RVR, and EOTR where a missing response will be imputed as a failure after performing the described imputation. All other endpoints will be presented using data as observed. For the change from baseline to each post-baseline time point in PT/INR, Fibrotest, and albumin, descriptive statistics will be calculated.

The number and percent of subjects who fail to suppress HCV RNA and received at least 6 weeks of treatment (active study drug duration \geq 36 days) will be tabulated along with the subject numbers corresponding to the subjects who failed to suppress.

The number of subjects who breakthrough at any time during treatment and within each protocol-specified visit (defined in Table 2) will be summarized along with a corresponding listing displaying the subject numbers at the first occurrence of breakthrough.

The number of completers (defined as study drug duration ≥ 77 days for subjects assigned to 12 weeks of treatment and ≥ 154 days for subjects assigned to 24 weeks of treatment) with final on treatment HCV RNA $< \text{LLOQ}$ who relapse within the SVR₄ window, within the SVR₁₂ window, within the SVR₂₄ window (defined in Table 3), after the SVR₂₄ window and anytime post-treatment (study drug end day ≥ 3) will be summarized along with a corresponding listing displaying the first occurrence of relapse. A similar table and listing will be provided of Preterm Relapses for subjects who do not complete treatment (defined as study drug duration < 77 days for subjects assigned to 12 weeks of treatment and < 154 days for subjects assigned to 24 weeks of treatment) with HCV RNA $< \text{LLOQ}$ at the Final Treatment visit.

The concordance between SVR₁₂ and SVR₂₄ will be assessed by agreement between SVR₁₂ and SVR₂₄ and by the positive predictive value (PPV) and the negative predictive value (NPV) of SVR₁₂ on SVR₂₄. The agreement between SVR₁₂ and SVR₂₄ is defined as the number of subjects achieving both SVR₁₂ and SVR₂₄ and the number of subjects not achieving both SVR₁₂ and SVR₂₄ out of all subjects in the ITT-II population. The PPV of SVR₁₂ on SVR₂₄ is the proportion of subjects who achieve SVR₂₄ out of all subjects who achieved SVR₁₂. The NPV of SVR₁₂ on SVR₂₄ is the proportion of subjects who do not achieve SVR₂₄ out of all subjects who do not achieve SVR₁₂.

